Outcomes, products and deliverables: Outcomes: The primary treatment outcome will be percent heavy drinking days of alcohol per week. The secondary outcome will be TBI symptom severity as measured by the Neurobehavioral Symptom Inventory (NSI). The exploratory outcomes will be levels of executive functioning (impulsivity, risk-taking, and decision making) and other neurocognitive domains assessed over the course of the study. *Products:* Data will be collected on 8 weeks of treatment plus week 12 follow-up. *Deliverables:*

This study is being sponsored by the Department of Defense (DOD) Telemedicine and Advanced Technology Research Center (TATRC).

II. RESEARCH PLAN

A. GOALS AND SPECIFIC AIMS

The overall goal of the project is to improve the care of veterans with traumatic brain injury and unhealthy alcohol use. We will conduct a pilot controlled clinical trial to assess the efficacy of N-acetylcysteine (NAC) to reduce alcohol use and improve brain injury symptoms in veterans with TBI who consume alcohol at *hazardous or harmful* levels. This project builds upon our current ITN-funded research on topiramate pharmacotherapy for unhealthy alcohol use in veterans with TBI.

A.1. PRIMARY AIMS:

Aims:

Measure both alcohol use and TBI symptom severity over the course of the 12-week study in order to detect differential efficacy of NAC and placebo. Alcohol use treatment outcome will be the Percent Days of Heavy Drinking (PHDD) of alcohol

A heavy drinking day is defined using NIAAA (2007) criteria: any day with 5 or more drinks per day for men or 4 or more drinks per day for women⁸. The choice of PHDD as the primary outcome is based on its endorsement by a recent NIAAA consensus conference⁹ and its increasing use in clinical trials ¹⁰⁻¹². TBI symptom severity will be measured with the Neurobehavioral Symptoms Inventory (NSI)^{13,14} a measure of postconcussive symptom severity.

Hypotheses:

Our **two primary** aims examine group differences, to detect differential efficacy of NAC vs placebo (*between-group analyses*). We will test the following hypotheses with between-groups analyses:

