- NAC treatment combined with Medical Management (MM) alcohol counseling will have greater efficacy than placebo in reducing percent heavy drinking days (PHDD). A heavy drinking day is defined using NIAAA (2007) criteria: any day with ≥5 drinks for men or ≥4 for women⁸. PHDD as primary outcome is based on recent NIAAA consensus⁹ and increasing use in clinical trials¹⁰⁻¹².
- **2.** NAC treatment will have a greater efficacy than placebo in reducing TBI related symptoms. TBI symptom severity will be measured by the Neurobehavioral Symptom Inventory (NSI)^{13,14}.

A.2. EXPLORATORY AIMS:

Exploratory Aims:

Other exploratory aims will include obtaining additional measures of alcohol use, executive functioning (e.g., impulsivity and risk taking) and other domains of neurocognition, and examining the potential moderating effect of rs6465084 on NAC treatment response

Hypotheses:

NAC treatment will have greater efficacy than placebo in: a) reducing other alcohol use measures (percent drinking days per week, drinks/week, drinks/drinking day, alcohol craving, biomarkers); b) improving neurocognition. We will examine neurocognitive domains which include executive functioning (impulsivity, risk-taking, decision making), auditory-verbal learning and memory, verbal fluency, processing speed and working memory. We will also explore the potential moderating effect of rs6465084 on NAC treatment response.

A.3. FUTURE PLANS

If the results of this pilot NAC HHAU/TBI project are positive, the investigators will seek funding for a larger controlled trial through the Department of Defense CDMRP and related funding programs and/or NIAAA R01 mechanisms. We believe that we can derive a reliable estimate of effect size for planning a randomized controlled trial from this small parallel groups controlled pilot study. It will be useful to obtain estimates of

variability for the key outcome variables in this population of comorbid patients in order to inform future controlled trials. Furthermore, we would seek to partner with other investigators in future studies to include neuroimaging to examine potential pre to post treatment neurobiological changes which may occur with NAC treatment.

B. BACKGROUND AND SIGNIFICANCE

B.1. OVERVIEW

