Review Medical Event Monitoring System (MEMS)	
Drug Accountability	
Dispense Medication	

D.5.c. Follow-up Phase

FOLLOW-UP PHASE The last visit, or follow-up, will take place on week 12. This visit will last between 3 and 3.5 hours.

FI. [name]
Measures
Concurrent Medications Form
Concurrent Treatments Form
AE Spontaneous Form
AE Checklist Form
TLFB – Timeline Followback
Demographics
CIWA – Clinical Institute Withdrawal Assessment for Alcohol, DSM-IV Version (CIWA-AD)
NSI – Neurobehavioral Symptom Inventory
AUDIT – Alcohol Use Disorders Identification Test
SIP-2R – Short Index of Problems
OCDS – Obsessive Compulsive Drinking Scales
PACS – Penn Alcohol Craving Scale
SHAS – Subjective High Assessment Scale
EVAR-B – Evaluation of Risks Scale
PCL – PTSD Checklist
POMS – Profile of Mood States
BDI-II – Beck Depression Inventory
BAI – Beck Anxiety Inventory
BIS-11 – Barrett Impulsivity Scale
PSQI – Pittsburgh Sleep Quality Index
ISI – Insomnia Severity Index
DERS – Difficulties in Emotion Regulation Scale
DTS – Distress Tolerance Scale
APT – Alcohol Purchase Task
WTAR - Wechsler Test of Adult Reading
HVLT-R – Hopkins Verbal Learning Test
TMT A + B – Trail Making Test A & B
WAIS 4 – Arithmetic
WAIS 4 – Antimetic WAIS 4 – Digit Span
Stroop Inhibition
COWA – Controlled Oral Word Association
BART – Balloon Analogue Risk Task
IGT – Iowa Gambling Task
SST – Stop Signal Task
AAT – Alcohol Approach Task
End of Study Completion Questionnaire
Procedures
Breath Alcohol Concentration (BrAC)
Clinical Labs – renal panel, hepatic panel and GGT
Ethyl Glucuronide (EtG)
Urine Drug Screen
Phosphatidylethanol (PEth)
Vitals (Blood pressure, heart rate, temperature)
Weight
Assess birth control method and perform urine pregnancy test (women only)
Drug Accountability
Dispense Medication

D.6. DATA ANALYSIS

The proposed study has primary, secondary, and exploratory outcomes.

D.6.a. Primary Outcome Measure

PI: [name] The primary outcome measure will be the change in number of drinking days from baseline to end of study, associated with NAC treatment.

1) Primary Hypothesis

The *Primary* hypotheses are that NAC treatment will be more efficacious than placebo in reducing PHDDs and TBI symptom severity (NSI).

2) Data Analytic Technique for the Primary Outcome

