Percent Heavy Drinking Days (PHDD): Negative binomial regression accommodates over dispersion and derives as an alternative to Poisson regression (most natural for analyzing count data). Heavy percent drinking days is often over-dispersed, positively skewed count data. Therefore, we will use random-intercept zero-inflated negative binomial model, modeling week (week 1 - week 8) as a continuous variable to analyze group differences in PHDD. *Neurobehavioral Symptom Inventory (NSI):* We will use random-intercept linear mixed models to explore the efficacy for NAC related reduction in TBI symptom severity measured by the NSI. Time period will be treated as a repeated effect, with correlations between time periods within participants modeled by an unstructured correlation matrix where appropriate. Model assumptions will be tested and required modifications will be performed. Both models will included fixed effect for week, treatment group (NAC and placebo), and the interaction between treatment group and week. Baseline alcohol consumption and NSI means will be used as respective covariates in group comparisons to control for pre-study and study enrollment effects.

3) Power Analyses for the Primary Outcome

We conducted a power analysis on our current pilot study of topiramate treatment of *alcohol dependence* in veterans with PTSD (see Section C.2.b.). For the outcome measure of percent drinking days (PDD), the effect size from the pilot data comparing week 12 to baseline within the topiramate group is d = 1.87. Because the proposed project is focused on veterans with TBI who have *hazardous* as well as harmful alcohol use, rather than just harmful use (alcohol dependence), we assume that the participants may start at a lower baseline level of DD in the proposed study than in the pilot study. This may not allow us to show as much improvement in the proposed study as in the completed pilot study of PTSD and alcohol dependence. Therefore, it would seem reasonable to target an effect size approximately half of what we found in our pilot study, i.e. d=0.9. A sample size of 16 for the topiramate arm of our proposed placebo-controlled pilot will allow us to detect a within-subjects effect size of d = 0.9, with 80% power at alpha = .05.

D.6.b. Exploratory outcomes/exploratory hypotheses

1) Exploratory Hypotheses

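### D.6.a names change in number of drinking days as the primary outcome, while the hypotheses and the only primary alcohol model use PHDD, and NSI and cognition each sit in two tiers

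*Combined protocol and SAP*

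**What the plan says.** D.6.a opens with: "The primary outcome measure will be the change in number of drinking days from baseline to end of study, associated with NAC treatment". The next item, D.6.a.1, gives the primary hypotheses as "NAC treatment will be more efficacious than placebo in reducing PHDDs and TBI symptom severity (NSI"). D.6.a.2, like the matching text in D.3.i, specifies one alcohol model, a random-intercept zero-inflated negative binomial model, "modeling week (week 1 - week 8) as a continuous variable to analyze group differences in PHDD". Its fixed effects are week, group and their interaction. The synopsis, A.1, the Timeline Followback entry in D.3.i and the purpose statement in D.4.d.1 also name PHDD as the primary alcohol outcome. A.2 puts drinking days among the exploratory hypotheses: "reducing other alcohol use measures (percent drinking days per week, drinks/week, drinks/drinking day, alcohol craving, biomarkers").

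The power paragraph, D.6.a.3, begins: "For the outcome measure of percent drinking days (PDD), the effect size from the pilot data comparing week 12 to baseline". It concludes: "A sample size of 16 for the topiramate arm of our proposed placebo-controlled pilot will allow us to detect a within-subjects effect size" of 0.9, with 80% power at alpha .05. D.3.i has a separate power statement: n=30, power .80, d about .65, one-tailed alpha .05.

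On tiers, the synopsis makes NSI the secondary outcome. A.1 lists it as the second of two primary hypotheses: "NAC treatment will have a greater efficacy than placebo in reducing TBI related symptoms". Cognition is exploratory in the synopsis, A.2, the exploratory paragraph of D.3.i and D.6.b. The multiple-comparisons rule in D.3.i and the DSMB list in E.2.e count it among the primary outcomes. D.3.i announces two tiers. D.6 announces three, but then contains only primary and exploratory subsections.

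**The concern.** An analyst who follows the sentence under the primary-outcome heading would report as primary a measure that A.2 calls exploratory, with no comparator and no primary model. The sentence is also hard to carry out. The baseline Timeline Followback covers 90 days in D.3.i, and both 12 weeks and 28 days in D.4.d.1, while later assessments cover 7 days. A change in a raw number of days needs a common window, and D.6.a gives none.

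The two quantities can move apart. D.6.a.3 builds its power case on drinking days too, so the problem reaches beyond one sentence. The stopping example in E.2.g depends on the primary alcohol outcome from baseline to study end, so it inherits the uncertainty about metric and time point. A.3 says the pilot's effect size will be used to plan a larger trial, which requires that the endpoint it describes be settled.

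**Working it through.** **Passages side by side**

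| Place | Alcohol primary | NSI | Cognition |
|---|---|---|---|
| Synopsis | PHDD per week | secondary | exploratory |
| A.1 and A.2 | PHDD | primary | exploratory |
| D.3.i, primary and exploratory paragraphs | PHDD | primary | exploratory |
| D.3.i, multiple comparisons | PHDD | primary | primary |
| D.6.a, opening sentence | change in number of drinking days | not mentioned | not mentioned |
| D.6.a.1 and D.6.b.1 | PHDD | primary | exploratory |
| D.6.a.3 | percent drinking days | not mentioned | not mentioned |
| E.2.e | alcohol use, metric not named | primary | primary |

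**Can the two alcohol measures diverge?** Table 2 (TBI group) gives 5.3 drinking days and 4.8 heavy drinking days per week, and 13.0 drinks per drinking day. In percent, 5.3/7 = 75.7% and 4.8/7 = 68.6%. A man at these means who cuts to 4 drinks on the same days falls below the 5-drink threshold. His PHDD goes to 0% and his drinking days stay at 75.7%. This is an illustration only: Table 2 describes veterans with AUD and PTSD from other trials.

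**The D.6.a.3 power figure.** Inputs: n = 16, within-subjects d = 0.9, alpha .05, sidedness not stated. For a paired t-test the noncentrality is d√n = 0.9 × 4 = 3.6 on 15 df. Power is 91.9% two-sided or 96.3% one-sided, so the stated 80% is not reproduced if d is standardised by the SD of change. If d is standardised by the raw SD, d for change = 0.9/√(2(1−ρ)). The two-sided detectable value at 80% power is 0.75, which requires √(2(1−ρ)) = 1.2, or ρ = 0.28. The documents give neither the standardisation nor ρ.

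**The D.3.i power figure.** Inputs: 30 participants at 1:1 (D.3.f), so 15 per arm; d = 0.65; one-sided alpha .05. For a two-sample t-test the noncentrality is 0.65 × √(15/2) = 1.78 on 28 df. Power is 53.7% one-sided (40.5% two-sided). The detectable d at 80% power is 0.93 one-sided or 1.06 two-sided. A d of 0.65 reaches 80.0% one-sided with 30 per arm.

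**Effect of repeated measures.** Assume a compound-symmetric 8-week mean with within-person correlation ρ, and d in single-week SD units. The SD of the mean relative to one week is √((1+7ρ)/8).

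- ρ = 0.3: √(3.1/8) = 0.622, and 0.93 × 0.622 = 0.58.
- ρ = 0.5: √(4.5/8) = 0.75, and 0.93 × 0.75 = 0.70.

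The range 0.58 to 0.70 contains 0.65. Both correlations are assumptions.

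**The case against.** The strongest defence is that PHDD is plainly the intended primary. It appears throughout, it has the only primary alcohol model, and the D.6.a sentence is an outlier in a document that still carries text from a topiramate trial. This stands as to intent, and it means the plan does not contain two competing primary tests. It does not remove a contradictory sentence under the governing heading, or the power paragraph built on drinking days.

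Several stronger readings are tempting, but the documents do not support them:

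- **A conflicting analysis window in the aims.** A reader might infer this from "over the course of the 12-week study in order to detect differential efficacy of NAC and placebo". That wording describes when alcohol use and symptoms are measured, and both are indeed collected at week 12. It does not set an analysis window against weeks 1 to 8.
- **A shifting alpha for PHDD.** With one, two or three primaries, plain Bonferroni gives 0.05, 0.05/2 = 0.025 or 0.05/3 = 0.0167. A reader might infer that the PHDD level moves accordingly. D.3.i speaks of separate families and a modified method, so PHDD could stay at 0.05. The unnamed variant and scope are a gap in their own right.
- **The 0.65 in D.3.i is wrong.** It fails only the single-measure benchmark. The planned model uses eight weekly measures and a baseline covariate.
- **The 80% in D.6.a.3 is miscalculated.** That depends on an unstated definition of d.
- **NSI must be primary.** The synopsis calls it secondary, and the analysis text says its model will explore efficacy. Either tier has textual support.

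**Conclusion.** The point stands and should be corrected. As written, D.6.a makes an unmodelled, elsewhere exploratory measure the primary outcome. The D.3.i multiplicity rule and E.2.e place an exploratory domain among the primaries, and NSI has two tiers. These are contradictions in current text and rest on no calculation.

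D.6.a.3 gives no power for the NAC versus placebo PHDD comparison: its metric, its contrast, its drug label and its arm of 16 all differ from the planned trial of 30 at 1:1. On a single-measure t-test with 15 per arm, detectable d is about 0.93 one-sided or 1.06 two-sided at alpha .05, and d = 0.65 has about 54% one-sided power. These are benchmarks, not the power of the planned model, which needs a definition of d and a within-person correlation that the documents omit.

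The time point also needs settling. D.4.b.6 ties study completion to the week 12 visit, outside the model's weeks 1 to 8. E.2.g refers to study end among participants who have completed treatment, without saying which visit it means.

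**What to change.** 1. Replace the opening sentence of D.6.a with: *Primary alcohol outcome: PHDD over treatment weeks 1–8, NAC vs placebo, tested with the model in D.6.a.2.* State whether the group term or the group-by-week term is the primary test. Label number or percent of drinking days, and any week-12 analysis, exploratory.
2. Have the sponsor choose one tier for NSI, either primary as in A.1 and D.6.a.1 or secondary as in the synopsis. Use it in the synopsis, A.1, D.3.i, D.6 and E.2.e, and make the lists of tiers in D.3.i and D.6 agree.
3. Remove cognition from the primary outcomes in the D.3.i multiplicity rule and in E.2.e. Name the modified Bonferroni variant, apply it to the remaining primaries, and state the level and sidedness.
4. Replace D.6.a.3 with a between-group PHDD statement for 15 per arm. In D.3.i, restate the 0.65 or give the repeated-measures assumptions behind it, including how d is standardised.
5. Reconcile the E.2.g wording on the primary alcohol outcome and study end with the adopted outcome and time point.

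The cost is wording and a less favourable stated power; no new data are needed. The changes should be made before outcome data are seen by arm. E.2.b and E.2.e provide for recurring outcome analyses for the DSMB in reports prepared by the PI, and the documents do not say whether these are shown by arm.

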Prospective participants will undergo a brief CPRS pre-screen (**see CPRS Screen**) and an in-person or telephone pre-screen (**see Phone Screen**) to establish that they are: 18-69 years of age, screen positive for TBI, drink at hazardous or harmful levels by NIAAA criteria⁸ and wish to reduce or stop alcohol use.

D.3.d. Consent

Breath Alcohol Test Prior to Consent

If the breath alcohol test reading is greater than 0.00%, the participant will be asked to return later that day, or on another day, to be retested.

Consenting

After passing the pre-screen, participants will provide written informed consent in compliance with IRB

PI: [name] regulations. During the consent process, Veterans are asked to abstain from driving to study visits while intoxicated. They are informed that if they do drive and their breath alcohol level is above 0.08, then a clinician will assess their safety before they are allowed to leave the SF VA Medical Center.

D.3.e. Screening

After consent, participants will be scheduled for screening assessments. The screening phase is accomplished over a total of approximately three to four visits extending over one week.

D.3.f. Random Assignment

Participants will be randomly assigned, sequentially as they qualify for the study, to either NAC or placebo in a 1:1 ratio per a computer-generated list provided by a biostatistician. Randomization will be balanced using permuted blocks. Participants and investigators will be blinded to assignment. To maintain the blind, sealed envelopes containing the study drug identification (e.g. NAC or placebo) will be kept together, in a limited access area (the study pharmacist's office) that will be available to the investigators should the blind need to be broken for any individual participant.

D.3.g. Pharmacotherapy

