The *Primary* hypotheses are that NAC treatment will be more efficacious than placebo in reducing PHDDs and TBI symptom severity (NSI). Data analytic technique: *Percent Heavy Drinking Days (PHDD):* Negative binomial regression accommodates over dispersion and derives as an alternative to Poisson regression (most natural for analyzing count data). Heavy percent drinking days is often over-dispersed, positively skewed count data. Therefore, we will use random-intercept zero-inflated negative binomial model, modeling week (week 1 - week 8) as a continuous variable to analyze group differences in PHDD. *Neurobehavioral Symptom Inventory (NSI):* We will use random-intercept linear mixed models to explore the efficacy for NAC related reduction in TBI symptom severity measured by the NSI. Time period will be treated as a repeated effect, with correlations between time periods within participants modeled by an unstructured correlation matrix where appropriate. Model assumptions will be tested and required modifications will be performed. Both models will included fixed effect for week, treatment group (NAC and placebo), and the interaction between treatment group and week. Baseline alcohol consumption and NSI means will be used as respective covariates in group comparisons to control for pre-study and study enrollment effects.

Exploratory Outcomes

Our exploratory hypotheses are that NAC treatment will be more efficacious than placebo in reducing other measures of alcohol use, producing significant improvement in cognitive performance (see section H.4.e), and will be moderated by rs6465084. Data analytic technique: Exploratory hypotheses will be analyzed in a parallel fashion, with separate negative binomial models applied to non-normally distributed count data and mixed linear models used for the remaining normally distributed outcome measures. Assumptions of each model will be tested and any required modifications will be performed. To investigate the potential moderating effect of rs6465084, we will use linear mixed models crossing treatment group with a two-level genotype group (A-allele vs. non A-allele carriers)^{110,121}, looking for a treatment group-by-genotype interaction on PHDD, and other secondary exploratory outcome measures of alcohol use.

Multiple Comparisons

Adjustment for multiple comparisons will be made for the separate families of primary outcomes (PHDD, NSI, cognitive performance) using a modified Bonferroni method¹⁶⁹.

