Estimates of NAC vs placebo for a larger study of HHAU and TBI.

We plan to derive a reliable estimate of effect for planning a large RCT from this small controlled pilot study. It will be useful to obtain estimates of variability in order to inform future controlled trials of NAC treatment for alcohol use. Our sample of n=30, with power of .80 will have the ability to detect an effect size of approximately .65 (one-tailed, alpha = .05). This is conventionally considered a medium effect size. To test for efficacy, we plan to implement intent-to-treat analyses, therefore including all participants randomized to trial. To examine estimates of harm, we will complete Per-Protocol analyses using data from participants exposed to study medications.

Study Limitations/Potential Problems.

Veterans Alcohol TBI PI: [name]

Recruitment, retention, missing data, and safety issues have been the most difficult hurdles facing clinical trials in AUDs. We believe that our research team is demonstrating a high level of success in recruiting (See Table 5) and retaining similar participants with TBI and HHAU, with 81% of participants completing the PI's pilot trial of TOP, a medication with a much higher adverse event profile¹²⁹. Similarly, there has been little missing data, with 81% of weekly study visits attended. Moreover, the use of a mixed-effects model allows for all available data in model estimation. Finally, human participant safety, although a prime concern, is relatively low in the use of NAC¹⁷⁰ (See Human Subjects Section)

I I. Da	[name]			
Table 5. Pl's current trial of				
topiramate in HHAU and mTBI				
Prescreened 255				
Screened (Signed Consent)	25			
Randomized	17 (53%)			
Percent Visits Attended	80.88%			
Percent Attended Week 12	81.25%			

D.3.j. Phlebotomy and Urine Drug Testing

Phlebotomy will be performed at screening, week 4, 8, and 12. Urine drug testing will be performed at screening, week 4, week 8, and week 12.

D.3.k. Participant Payment

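### The PHDD model has a random intercept only, so if participants' trajectories differ materially, the standard error of its group-by-week term is too small

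*Combined protocol and SAP*

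**What the plan says.** The PHDD model is given twice in the same terms, in D.3.i (Statistical Plan and Data Analysis, Primary Outcome) and in D.6.a, item 2. It is a "random-intercept zero-inflated negative binomial model, modeling week (week 1 - week 8) as a continuous variable". On fixed effects the plan says: "Both models will included fixed effect for week, treatment group (NAC and placebo), and the interaction between treatment group and week". Baseline alcohol consumption is a covariate.

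Two other sentences bear on the within-person structure:

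- Correlations between time periods are to be "modeled by an unstructured correlation matrix where appropriate". This follows the description of the Neurobehavioral Symptom Inventory (NSI) model and its repeated time-period effect. Only the later fixed-effects sentence is addressed to both models.
- "Model assumptions will be tested and required modifications will be performed". This names no test, threshold or remedy.

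Neither section says whether the group coefficient, the interaction or a joint test decides the PHDD hypothesis. The only sidedness given for a between-group comparison is in the paragraph on estimates for a larger study: "Our sample of n=30, with power of .80 will have the ability to detect an effect size of approximately .65 (one-tailed, alpha = .05").

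**The concern.** A random intercept lets participants differ in level but gives everyone in an arm the same slope. With week continuous and group-by-week in the model, the interaction compares two average slopes, and the relevant noise is how much slopes vary between people. If some participants cut down steadily and others do not, the model files that variation under independent weekly error, and the interaction looks more precise than it is.

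The group coefficient is not automatically safe. Nothing says week is centred. Coded 1 to 8, the group coefficient is the difference extrapolated to week 0. That equals the difference at the mean week, 36/8 = 4.5, minus 4.5 times the slope difference, so it inherits the slope's error.

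This matters for the pilot's stated purpose. A.3 and D.3.i both want a reliable effect estimate and estimates of variability for planning a larger trial. An interval that is too narrow misleads that planning, and a model without a slope variance cannot report one.

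**Working it through.** **Plan's own figure.** The plan gives no power or error rate for the group-by-week term, so there is nothing to reproduce on this exact point. Its between-group figure (d about 0.65, 80% power, one-tailed 5%) concerns a standardised effect size. At 15 per arm, d = 0.65 gives power of 0.54, and 0.80 is reached only with 30 per arm. That is a separate matter and is not used below.

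**Inputs from the documents.** 30 participants allocated 1:1 (D.3.f), so 15 per arm. Eight weekly 7-day windows (D.4.d.1).

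**Assumed inputs.** Slope SD *t* between participants: 0.1, 0.2 and 0.3 heavy days/week per week. Residual SD *s*: 1.0, 1.5 and 2.0 heavy days/week. Neither is in the documents. Table 2 in C.5 gives a baseline mean and SD of 4.8 ± 1.9 heavy days/week for the TBI group, which is cross-sectional and says nothing about slopes.

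**Closed form, linear scale.**

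1. For weeks 1 to 8, Sxx = 2(0.5² + 1.5² + 2.5² + 3.5²) = 42.
2. True variance of the slope difference: (2/15)(t² + s²/42) = (2/15)(s² + 42t²)/42.
3. Under a random intercept only, slope variation is spread over 7 within-person degrees of freedom. The residual variance becomes s² + 42t²/7 = s² + 6t², and the model's variance is (2/15)(s² + 6t²)/42.
4. Ratio R = (s² + 42t²)/(s² + 6t²). Actual error is 2[1 − Φ(1.96/√R)] two-sided and 1 − Φ(1.645/√R) one-sided.

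Example: s = 1.5 and t = 0.2 give R = 3.93/2.49 = 1.578, √R = 1.256, and two-sided error 2[1 − Φ(1.560)] = 11.9%.

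| Slope SD | s = 2.0, two-sided | s = 1.5, two-sided | s = 1.0, two-sided | s = 1.5, one-sided |
|---|---|---|---|---|
| 0.1 | 6.0% | 6.8% | 9.0% | 6.3% |
| 0.2 | 9.0% | 11.9% | 18.2% | 9.5% |
| 0.3 | 13.4% | 18.2% | 26.6% | 13.2% |

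A linear null simulation at s = 1.5 gives 6.6%, 11.7% and 18.2% two-sided. With a participant-level variance on 28 df it gives 4.6% to 4.9%.

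**The planned model itself.** A random-intercept zero-inflated negative binomial model was fitted to 600 simulated null trials per setting (15 per arm, 8 weeks; Monte Carlo error about 2 to 3 points). Two-sided error of the group-by-week Wald test was:

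| Data generated as | Slope SD (link scale) | Error |
|---|---|---|
| Negative binomial counts | 0 / 0.05 / 0.1 / 0.2 | 6.5 / 7.7 / 9.3 / 20.0% |
| Bounded 0 to 7 counts | 0 / 0.1 / 0.2 / 0.4 | 3.0 / 4.5 / 9.7 / 22.7% |
| Percent 0 to 100 treated as a count | 0 / 0.1 / 0.2 / 0.4 | 5.3 / 6.0 / 9.7 / 17.3% |

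The dispersion and zero-inflation terms do not absorb clear slope variation. With bounded counts and small slope variation, the model's standard error is if anything slightly large (1.10 and 1.04 times the true one at slope SD 0 and 0.1).

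**After adding a random slope.** These rest on 242 and 207 usable fits, with Monte Carlo error of about 4 points.

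- Negative binomial, slope SD 0.2: two-sided error falls from 20.0% to 9.5%, or 8.7% with t on 28 df. One-sided it falls from 13.8% to 7.4%.
- Bounded counts, slope SD 0.4: two-sided error falls from 22.7% to 8.2%, or 7.7% with t on 28 df. One-sided it falls from 15.2% to 11.1%.

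The two-sided excess is more than halved but not clearly removed.

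**The case against.** The strongest objection is that the size is unknown. Both SDs are assumed, and bounded weekly counts with little slope variation showed no inflation. That stands. A reader might infer that the nominal 5% test is certainly not a 5% test, but the documents give no slope variance and cannot support that.

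A reader might also take 0.3 as the expected slope SD: from 4.8 heavy days/week, if half the sample falls evenly to near zero (about 0.6 per week over 8 weeks) and half does not change, the SD is about 0.3. That is an extreme mixture. D.3.h has participants advised at the first visit to stop drinking. If those who respond do so early, most of the difference is in level, which the random intercept captures. The 0.3 figure is the far end of a range.

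Third, the interaction is not named as the decisive test. If the contrast were the average group difference over weeks 1 to 8, then with complete linear data the slope term cancels, because deviations from week 4.5 sum to zero, and the random intercept suffices. So a reader should not infer that every group comparison from this model is affected. The plan neither names that contrast nor centres week.

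Fourth, the assumption-testing sentence permits a random slope. It does, but choosing the random structure after seeing the data is what pre-specification should prevent.

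Finally, a pilot carries less weight on type I error. That is fair, though a too-narrow interval still matters for planning the next trial.

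**Conclusion.** The concern holds as a conditional one. Followed as written, the PHDD model understates the standard error of the group-by-week term if participants' slopes differ materially.

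At 15 per arm and slope SDs of 0.1, 0.2 and 0.3 heavy days/week per week, two-sided error is about 7%, 12% and 18% at residual SD 1.5. The range runs from 6%, 9% and 13% at residual SD 2.0 to 9%, 18% and 27% at 1.0. One-sided, matching the only sidedness stated, it is about 6%, 10% and 13% at residual SD 1.5. These are linear-scale figures on assumed SDs. Fits of the planned model show the same pattern, with no inflation for bounded counts when slope variation is small.

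The unstructured-correlation wording does not rescue PHDD, since it belongs to the NSI model. It would also be too much to infer that a random slope alone restores the nominal rate: in the planned model about 8% to 9.5% two-sided error remained, so a small-sample correction is needed too.

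**What to change.** In D.6.a and the matching text in D.3.i:

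1. State which group contrast decides the PHDD hypothesis.
2. Centre week, so that the group coefficient is not a week-0 difference.
3. Add a participant-level random slope for week, and use a small-sample reference distribution, for example t on about 28 df.
4. Pre-specify the fallback if the model does not converge: the random-intercept model with participant-level cluster-robust or cluster-bootstrap standard errors and the same small-sample correction.

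Because some excess error remained in the simulations even with t on 28 df, the interval should be reported with that caution.

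The cost is SAP wording only; no visit or data item changes. The downside is a somewhat wider interval and, with 30 participants, a real chance that the fallback is used.
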